**C.5.3.2. Down-titration of Study Drug**

During the washout period, after treatment period 2 (Table 5) or if it is necessary for a subject to stop the study drug, the subject should optimally be weaned off the drug as follows. Per manufacturer's guidelines, carvedilol will be down-titrated over one week:

- Day 1: 50% of previous dose
- Day 3-5: 25 % of regular dose
- Day 7-10: Stop drug

In the event of severe clinical instability or inability to take the study drug (i.e., severe vomiting), weaning may need to occur over a shorter period of time, at the discretion of the study physician and care providers. Reinitiation of study drug will be considered

after the PI has consulted with the study participant (or legal guardians) and attending cardiologist.

#### **C.5.3.3 Protocol Deviations in Treatment**

All deviations from the above schedules will be noted and described on a study report form. In addition, for all non-study drugs, the dosage, treatment period, and reason for use will be recorded. For modified and interrupted therapy, the length of and reason for the modification/interruption will be recorded. Every attempt will be made to keep protocol deviations and non-protocol treatment to a minimum.

#### **C.5.3.4 Dispensing of Study Drug and Compliance Monitoring**

All study drugs (placebo and carvedilol) will be dispensed through the investigational drug pharmacy at Children's Medical Center of Dallas.

Pill Dispensing: The family will receive a medication bottle. Study drug in the form of pills will be dispensed by the pharmacy at visits 1, 2, 3, 4, 7, 8, 9, and 10.

Unused study drug will be returned to the pharmacy to monitor compliance. Study drug compliance will be assessed by comparing the expected to the measured number of doses in pill form of study drug returned.

Once measurement the pill count by the pharmacy is complete, the pharmacy will destroy the returned study medication according to standard operating procedure.

#### **C.5.3.5 Subject Monitoring**

Subjects will be monitored for adverse events at each study visit. If, during the study, the study investigator determines that the subject has developed an adverse reaction, further monitoring will be performed as clinically indicated.

#### **C.5.4 Indications for Permanent Discontinuation of Study Drug**

- Intolerance to study drug
- Continued administration of study drug felt to be not indicated by the attending cardiologist or study investigator
- Pregnancy or planned pregnancy
- Other adverse events that require discontinuation of study drug in the judgment of the study investigator

The reason and the circumstances for permanent discontinuation of study drug will be documented. If study drug is permanently discontinued, the subject will continue to be followed and undergo expected tests and measurements through the planned completion date (31 weeks after randomization), unless an indication for withdrawal from trial is met.

#### **C.5.5 Indications for Withdrawal from the Trial**

- Subject/guardian refusal to continue in the trial, including refusal of the subject to sign the adult informed consent form upon reaching the age of consent
- Subject failure to return for scheduled appointments

The reason for withdrawal and the circumstances of withdrawal will be documented for all subjects withdrawn from the study.

#### **C.5.6 Trial Completion**

Subjects will be considered to have completed the study if they have completed the assessment scheduled for  $31 \pm 2$  weeks post-randomization. Down-titration of the study drug will be performed as described in C.5.3.2.

#### **C.5.7 Other Treatments/Interventions**

Subjects will receive non-study medical care as recommended by their cardiologist and other care providers. The need for additional procedures and all prescription medications will be recorded on study forms

## **C.6. Potential Risks, Benefits, Adverse Events and Protections**

### **C.6.1. Potential Risks**

The possible risks or discomforts to the subjects include those listed below.

1. Treatment with carvedilol may rarely induce adverse drug reactions including symptomatic bradycardia, dizziness, postural hypotension, fatigue, lethargy, mental depression, headache, nausea, diarrhea, sleep disturbances, and asthma exacerbation.
3. Self-limited exercise tests pose very small risks of syncope, arrhythmias, hypotension, emesis, dizziness, leg or other muscle cramping.
4. Risks associated with drawing blood from a vein include momentary discomfort and/or bruising. Infection, excess bleeding, clotting, and fainting are also possible, although unlikely. Less than 5 ml of blood is needed for the 3 safety laboratories (CBC, CMP, and BMP).
5. Study investigators from UT Southwestern and Children's Health will have access to the medical record for 5 years after each subject completes the study to review the results of follow-up clinical course, surgical intervention, and other relevant studies.

### **C 6.2 Protection Against Risks**

Protection of study subjects is implicit in all studies at UT Southwestern and Children's Medical Center of Dallas, and is achieved through sound study design, patient education, strict adherence to informed consent principles, careful monitoring of subjects, and compliance with International Conference on Harmonisation (ICH) Good Clinical Practices, including HIPAA regulations or local national laws and regulations.

#### **C.6.2.a Informed Consent**

Consent will be obtained from the parent(s) or legal guardian and consent or assent, as applicable, will be obtained from the subject. This will be facilitated by IRB-approved study brochures, and information about the trial that will be placed on the clinical trials Web site, [www.clinicaltrials.gov](http://www.clinicaltrials.gov). The site study investigators, study coordinators, or assigned designees will obtain consents, documented by the subject, parent(s) or legal

guardian's witnessed signature on an informed consent document that is compliant with HIPAA regulations and local and national laws and regulations. The potential study participant will be informed of possible adverse effects from carvedilol some of which are transient, including: fatigue (20%), bradycardia (9%), hypotension (9%), syncope (3%), dizziness (6%), chest pain (2%), nausea (9%), vomiting (6%), cough (8%), insomnia (3%), headache (8%). If potential subjects or parents decline to participate, their or their child's medical care will not be adversely affected in any way. If they agree to participate, they are free to withdraw from the study at any time. Additionally, subjects who reach the age of consent during their participation in the trial will be re-consented with the adult informed consent form.

#### **C.6.2.b Protection Against Risks**

To minimize the potential risks listed in Section C.6.1 the following steps will be taken:

1. The starting doses of carvedilol will be low and will be up-titrated carefully (see Table 1).
2. Subjects with known renal dysfunction will be excluded from the study.
3. Blood draws, to the extent possible, will be performed after the application of a topical anesthetic cream.
4. Serum creatinine, BNP, hemoglobin, hematocrit, AST and ALT will be measured as during the screening phase. Serum creatinine, BNP, AST and ALT will be measured during the treatment phase (Table 5).
5. Pregnancy or a planned pregnancy during the trial are exclusion criteria. A urine pregnancy test will be obtained during the screening phase. A statement regarding the potential risk of one of the study drugs will be given to female subjects of child-bearing potential and to the parents of female subjects less than 18 years of age. They will be asked questions about the subject's sexual activity. In addition, this risk is listed in the consent and the assent. Written documentation of birth control measures will be required for female subjects who are sexually active.
6. The study sponsor will pay for all testing that is not part of routine care.

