### **B.5.4 Pregnancy Test**

Carvedilol is classified as pregnancy class C. Rat models have shown increased chance of skeletal developmental delay. However, this occurred only when rats were given 50 times the current recommended dose. There are currently no adequate studies assessing safety during pregnancy and therefore pregnant patients will be excluded.

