#### **C.2.1.c Exclusion Criteria Screening Phase**

To be eligible for this trial, the subjects must meet none of the following exclusion criteria at the time of enrollment:

- 1) The use of beta blockers within 2 months of randomization
- 2) Patients actively listed for transplantation at time of entry into the study or anticipated to undergo heart transplantation, interventional catheterization, or corrective cardiac surgery during the 7 months following entry into the study
- 3) Sustained or symptomatic ventricular dysrhythmias uncontrolled by drug therapy or the use of an implantable defibrillator, and/or significant cardiac conduction defects, e.g., 2nd degree or 3rd degree AV block, or sick sinus syndrome, unless a functioning pacemaker is in place

- 4) Uncorrected obstructive or severe regurgitant valve disease, nondilated cardiomyopathy, or significant systemic ventricular outflow obstruction
- 5) Known renovascular hypertension or evidence of pulmonary hypertension (pulmonary vascular resistance > 6 Wood units) unresponsive to vasodilator agents such as oxygen, nitroprusside, or nitric oxide
- 6) History or current clinical evidence of moderate-to-severe fixed obstructive pulmonary disease or severe reactive airway diseases (e.g., asthma) requiring hospitalization within the past 2 years or patient currently using long-term inhaled bronchodilators
- 7) Renal, hepatic, gastrointestinal, or biliary disorder that could impair absorption, metabolism or excretion of orally administered medication
- 8) Concurrent terminal illness or other severe disease (e.g., active neoplasm) or other significant laboratory value(s) which, in the opinion of the investigator, could preclude participation or survival
- 9) Endocrine disorders such as primary aldosteronism, pheochromocytoma, hyper- or hypothyroidism, insulin-dependent diabetes mellitus
- 10) Unwillingness or inability to cooperate, or for the parents or guardians to give consent, or for the child to give assent, or any condition of sufficient severity to impair cooperation in the study
- 11) Pregnancy or possible pregnancy at time of randomization, or female of child bearing potential who are lactating, or sexually active and not taking adequate contraceptive precautions (e.g., intrauterine device or oral contraceptives for 3 months prior to entry into the study)

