**Table 4. Screening Measures**

Screening Phase	
	Visit 0 (week -2-0)
Exercise Test	x
Pregnancy Test	x*
BNP, CBC, CMP	x

\*to be performed on females of child bearing age only (12 years of age or older)

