**Table 5. Treatment Phase Measures**

Treatment Period 1 (week 0-12)						
	Visit 1 (week 0)	Visit 2 (week 1)	Visit 3 (week 2)	Visit 4 (week 3)	Visit 5** (week 8)	Visit 6 week 12
Duration (hrs)	1-1.5	<1	<1	<1	<1	2
Vital signs	x	x	x	x		x
NYHA HF Classifications	x	x	x	x		x
Adverse Drug Effect	x	x	x	x	x	x
Compliance Check		x	x	x	x	x
Safety Labs (CMP, BNP, CBC)	X					x
Exercise Test	x*					x
Study Drug Medication	X_initiate	X- uptitration 1	X- uptitration 2	X-no change		X-after visit stop study medication***
Washout Period (Week 13-18)						
Treatment Period 2 (week 19-30)						
	Visit 7 (week 19)	Visit 8 (week 20)	Visit 9 (week 21)	Visit 10 (week 22)	Visit 11** (week 26)	Visit 12 (week 30)
Duration (hrs)	2	<1	<1	<1	<1	2
Vital Signs	x	x	x	x		x
NYHA HF Classifications	x	x	x	x		x
Adverse Drug Effect	x	x	x	x	x	x
Compliance Check	x	x	x	x	x	x
Safety Labs (CMP, BNP, CBC)	X					x
Exercise Test	x					x
Study Drug Medication	X-initiate	X- uptitration 1	X- uptitration 2	X-no change		after visit stop study medication***

\*-exercise test from screening phase may be used if visit 1 exercise test if done within 14 days of visit 1,

\*\*-may be phone visit

\*\*\*dose of study medication decreased during weeks 6 and 31 and then stopped

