### C.7.7 Laboratories

CBC, CMP and BNP will be performed as part of the screening phase (Visit 1) as previously outlined. CMP, BNP will be performed at visits 6, 7, and 12. All laboratories will be drawn at the Children’s Medical Center by a medical professional experienced in phlebotomy. As previously mentioned, topical anesthetic will be used when deemed appropriate. After proper labeling, blood will be sent to the Children’s Medical Center laboratory for immediate analysis. Urine pregnancy tests will be performed only on female participants 12 years of age and will be performed at Children’s Medical Center during the screening phase.

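### The only scheduled pregnancy test is at screening, so placebo-first females start study carvedilol at Visit 7 on a test 18 to 22 weeks old

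*Combined protocol and SAP*

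**What the plan says.** Section B.5.4 gives the reason for excluding pregnancy: "There are currently no adequate studies assessing safety during pregnancy and therefore pregnant patients will be excluded". Exclusion 11 in C.2.1.c covers "Pregnancy or possible pregnancy at time of randomization", and also sexually active females without adequate contraception. Section C.6.2.b goes beyond the time of entry: "Pregnancy or a planned pregnancy during the trial are exclusion criteria". Section C.5.4 makes pregnancy or planned pregnancy a reason to stop study drug permanently.

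Testing is scheduled once. Section C.6.2.b says "A urine pregnancy test will be obtained during the screening phase". Table 4 places the test at Visit 0 (weeks -2 to 0) for females aged 12 or older. Section C.7.7 says "Urine pregnancy tests will be performed only on female participants 12 years of age"; the word 'only' there limits who is tested, and the rest of that sentence places the test in the screening phase. Table 5, the schedule for Visits 1 to 12, has no pregnancy row, and its safety laboratories are CMP, BNP and CBC.

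The other safeguards in C.6.2.b are a risk statement, questions about sexual activity, and this requirement: "Written documentation of birth control measures will be required for female subjects who are sexually active". No schedule is given for repeating the questions or the documentation.

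**The concern.** A single test before randomization suits a parallel-group trial in which active drug starts straight away. Here everyone crosses over. Eligibility is confirmed once, before randomization (C.5.2), but the placebo-first sequence does not meet study carvedilol until Visit 7, after a 12-week placebo period and a washout. The reason given in B.5.4 for excluding pregnant patients applies just as much to a first dose in week 19 as to one in week 0, yet only the carvedilol-first sequence has a recent test.

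A placebo-first participant who became pregnant after screening could start carvedilol at Visit 7 and be up-titrated at Visits 8 and 9 with no scheduled procedure to reveal it. The adverse-reaction symptom list in C.7.6 has no pregnancy item. Because treatment is masked (C.5.1), investigators cannot tell who is starting carvedilol at Visit 7, so they cannot direct an informal test to the right participants. A girl aged 11 at screening who turns 12 before Visit 7 would never be tested, although Table 4 treats 12 as child-bearing age.

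**Working it through.** The documents state no test age, so there is no figure to reproduce. The check is arithmetic on the visit schedule.

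**Inputs**
- Screening at weeks -2 to 0 (Table 4); treatment begins within 14 days of screening (C.4).
- Visit 6 at week 12, Visit 7 at week 19, Visit 12 at week 30 (Table 5).
- Windows: plus or minus 7 days for Visit 7, plus or minus 14 days for Visits 6 and 12 (C.7.2).
- Target of 30 enrolled (C.8.2), 1:1 allocation (C.5.2), 50% female (C.3.1).

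**Age of the test** = visit week (with its window) + weeks from screening to week 0 (0 to 2)

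| | Carvedilol-first | Placebo-first |
|---|---|---|
| First study carvedilol | Visit 1: 0 to 2 weeks | Visit 7: 18 + 0 = 18 to 20 + 2 = 22 weeks |
| End of carvedilol period | Visit 6: 10 + 0 = 10 to 14 + 2 = 16 weeks | Visit 12: 28 + 0 = 28 to 32 + 2 = 34 weeks |

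Without the window, the age at Visit 7 is 19 + 0 = 19 to 19 + 2 = 21 weeks. Counting Visit 1's own 7-day window separately widens the range to 17 to 23 weeks. C.7.7 labels the screening laboratories Visit 1 where Table 4 has Visit 0. If the test were done at Visit 1 (week 0), its age at Visit 7 would be 18 to 20 weeks. The conclusion is the same in each case.

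**Females affected**
- Expected placebo-first females: 30 x 0.5 x 0.5 = 7.5, if 30 are randomized and all reach Visit 7.
- This is an expectation, not a ceiling. With 15 placebo-first participants, the number of females is Binomial(15, 0.5): P(4 to 11) = 1 - 2 x 576/32768 = 0.965, and P(9 or more) = 9949/32768 = 0.304.
- The documents give no age distribution. If ages were uniform over 10 to 35 (an assumption), the share aged 12 or older would be 23/25 = 0.92, giving 7.5 x 0.92 = 6.9.

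These are counts of females who pass through the gap, not of expected pregnancies.

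**The case against.** The case against giving this much weight has five parts.

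- **Prevention is substantial.** The protocol excludes possible as well as confirmed pregnancy, excludes sexually active females without adequate contraception, asks about sexual activity, informs participants and parents of the risk, and requires written proof of birth control. Those truly at risk at Visit 7 are females whose contraception failed, who became sexually active after entry, or who did not disclose.
- **The count is not the risk.** The 7.5 includes females who are not sexually active and those on documented contraception. Without rates of sexual activity, contraceptive failure or pregnancy, harm cannot be sized.
- **Evidence of harm is limited.** B.5.4 reports skeletal delay in rats only at 50 times the recommended dose.
- **The randomization-time exclusion is not breached.** Exclusion 11 is framed at randomization, and the protocol applies it then.
- **The remedy is partial.** Pregnancy can also begin during either 12-week treatment period, and one test at Visit 7 would not find it.

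All five are fair as limits, and the second means the clinical weight stays unquantified. They do not remove the gap. Prevention and disclosure do not detect a pregnancy. B.5.4 rests the exclusion on the absence of adequate studies, so the rat finding does not answer it. C.6.2.b also carries the pregnancy exclusion through the trial, beyond randomization. Visit 7 is singled out because it is a first exposure to study carvedilol without the recent test that the other sequence receives.

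**Conclusion.** The concern holds. Placebo-first females first receive study carvedilol on a pregnancy test 18 to 22 weeks old, against 0 to 2 weeks in the carvedilol-first sequence. This follows directly from the schedule and visit windows and needs no clinical assumption. About 7.5 females are expected to be affected, on the assumptions of 30 randomized, half female and no losses before Visit 7; non-completion would lower the number. Absolute risk is probably small given the contraception rules, but it cannot be estimated from the documents. This should be fixed: the protocol itself rules out exposure in pregnancy, and the correction is cheap.

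**What to change.** Add a urine pregnancy test to the Visit 7 column of Table 5 for females aged 12 or older, judging age at that visit. Require a negative result before Period 2 drug is dispensed. Test both sequences so that masking is kept. Amend C.6.2.b and C.7.7 to match; a positive result would invoke the existing discontinuation rule in C.5.4.

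The cost is a short protocol amendment and about 30 x 0.5 = 15 inexpensive urine tests in expectation if all reach Visit 7, or 15 x 0.92 = 13.8 with the age-12 threshold under the uniform-age assumption. Visit 7 is already a two-hour visit with an exercise test, blood draw and dispensing, so no visit is added. C.6.2.b already commits the sponsor to pay for testing outside routine care. The change covers entry to Period 2 only; detecting a pregnancy that begins during a treatment period would need further on-drug tests.

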### **C.6.3 Potential Benefits of the Proposed Research**

The possible benefits of participation in the proposed study to the subject are:

1. The subject's family, primary care provider, and cardiologist will receive extensive information regarding the subject's cardiac status.

### **C.6.4 Risk/Benefit Ratio**

The risk/benefit ratio of the study is favorable. The risk of adverse drug reactions is low, and most are relatively minor in nature and reversible with a decrease in the dose of study drug or cessation of therapy. There is a small risk of privacy being compromised in this study. Subject identities will be coded to insure confidentiality and all data will be stored and communicated according to the code to protect against loss of privacy. There will be some unavoidable inconvenience to subjects and families because of study visits and blood draws. However, subjects and families will be compensated within the limits of the study budget and local IRB guidelines for travel and related expenses for study visits. All study costs not related to standard clinical care will be paid for. Given the anticipated benefits to subjects and others with the Fontan circulation, the risks are reasonable.

### **C.6.5 Importance of Knowledge to be Gained**

Current data are very limited to support or refute the utility of carvedilol in this population. The variable practices in the use of carvedilol in management of SV patients underscore the need for further research. Data collected in the proposed study will provide important information regarding safety profile, as well as efficacy data crucial to the development of multicenter trials of carvedilol in Fontan patients.

### **C.6.6 Data and Safety Monitoring Plan**

Throughout the performance of this study and during the performance of all procedures, subjects will be carefully monitored in accordance with current medical practices. Treatment with carvedilol as proposed in this study has had few if any reported side effects. Based upon the extensive experience with all aspects of the study protocol procedures, it is anticipated that that the risk of adverse events associated with the

study will be acceptably low and therefore will be monitored by the PI, the DSMB (see below), and the IRB. Maximum efforts will be undertaken to ensure the safety of all study participants. All personnel involved in performance of the study and its procedures will be fully trained and extensively experienced. All serious adverse events will be required to be reported to the IRB within 24 hours of it being brought to the attention of the attending physician of the subject as well as the principal investigator of the study. The DSMB will oversee progress and safety of the project and will consist of a congenital heart disease specialist, pediatric pharmacist and statistician. The DSMB will meet every 6 months to review the study. Non severe adverse events will be reported according to IRB protocol.

A major component of safety monitoring is ascertainment and reporting of adverse events, including adverse drug reactions. The approach to these activities for this trial is summarized in the sections that follow.

#### **C.6.6.a Definition of Adverse Event and Adverse Drug Reaction**

International Conference on Harmonisation Good Clinical Practice guidelines define an *adverse event* as any untoward medical occurrence experienced by a subject administered a pharmaceutical product, regardless of its causal relationship to the study treatment. An event can be any unfavorable and unintended sign, symptom, laboratory abnormality, or disease temporally associated with the use of the product. An *adverse drug reaction* is a response to a drug that is noxious and unintended, and that occurs at doses normally used in humans for prophylaxis, diagnosis, or therapy of disease or for modification of physiological function.

